### 4.2.2 **Prior and Concomitant Medications**

The number and percentage of subjects receiving each medication (by Anatomical Therapeutic Chemical (ATC) classification system codes and generic name) will be presented by treatment for the FAS. Separate tables will be presented for all medications received during the following periods:

- Prior: Medications with a stop date  $\leq$  the first day of IP.
- Concomitant during treatment: Medications that are still ongoing on the first day of IP and also medications with start date ≥ the first day of IP and ≤ the last day of IP + 2 weeks.
- Post –treatment: Medications that are still ongoing one day after (the last day of IP + 2 weeks) and also medications with start date > the last day of IP + 2 weeks and ≤ Visit 11 (Week 26).

Tables for maintenance medications (started prior to and ongoing after the first day of IP) will be produced displaying the baseline total daily dose of ICS. The number of subjects using other maintenance asthma medications at baseline will also be summarized. In addition, the total number of days of systemic corticosteroid treatment associated with asthma exacerbations per subject from the first day of IP up to Week 12 will also be summarized.

A separate table will be presented for subjects who take disallowed concomitant medications. Disallowed medications will be defined using a combination of programming and a physician review (prior to database lock) of the unique combinations of ATC code classifications and generic terms captured.

Medications will be classified according to the AstraZeneca Drug Dictionary. Percentages will be calculated relative to the number of subjects in the FAS.

All medications will also be listed by subject for the FAS.

Data from subjects who discontinued IP but remain in the study, where possible and relevant, will be included in the appropriate medication summaries.

### 4.2.3 Exposure and Compliance

Extent of exposure to IP is defined as the number of days between the start and the end dates of study therapy plus 14 days:

Extent of exposure (days) = (Last dosing date + 14 days) - First dosing date + 1.

In addition, the total number of dosing occasions is calculated by summing the doses taken by the subject. The total number of dosing occasions expected is defined as:

*Total number of dosing occasions expected = number of visits during treatment phase the subject attended.* 

Compliance is defined as:

Compliance (%) = (Total number of dosing occasions/total number of dosing occasions expected) x 100

Extent of exposure to IP, compliance and total number of dosing occasions will be summarized by treatment group, using the safety analysis set.

Compliance with the regularly scheduled ICS/LABA asthma inhaler as recorded in the daily diary will be summarized by each bi-weekly period and treatment group, together with the compliance of the use of the daily diary.

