#### **Duration of treatment**

After initial enrolment and confirmation of entry criteria (Visit 1) subjects will proceed to a run-in period of 4 weeks during which their suitability for randomization will be confirmed. The subjects' currently prescribed ICS and additional asthma controller medication will remain unchanged during the run-in and treatment period.

Subjects who meet all the eligibility criteria at Visit 3c will be randomized to a 12-week treatment period and receive either tralokinumab or placebo as an investigational product (IP) in addition to their existing asthma controller medications. IP will be administered at weeks 0, 2, 4, 6, 8 and 10 (Visit 3c to Visit 8). End of treatment (EOT) visit will be at week 12 (Visit 9).

Post-treatment follow-up period for all subjects will be for 14 weeks after the EOT visit with a telephonic follow-up (FU) 1 visit (Visit 10, Week 16). There will be an on-site FU 2 visit (Visit 11, Week 26) only for WOCBP to also ascertain their pregnancy status. For all other subjects this will be a telephonic FU 2 visit

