# 4.2 Treatment period

The randomized treatment period begins at Visit 3c (Week 0) till Visit 8 (Week 10) with End of treatment (EOT) visit at Visit 9 (Week 12). Subject's eligibility to continue in the study will be once again confirmed before randomization during Visit 3c (see Section 3.1 and 3.2). Assessments and procedures to be performed during the treatment period are as per Table 1.

Subjects confirmed to be eligible will be randomized in a 1:1 ratio to receive either tralokinumab 300 mg or placebo every two weeks throughout the treatment period. The first

dose of the IP will be administered at Visit 3c after the subject's randomization via IVRS/IWRS.

Following randomization the subject will receive the double-blind treatment for 12 weeks, with the last dose of tralokinumab /placebo administered at Visit 8 (Week 10).

Subjects will continue on their current ICS and other maintenance asthma controller medications (if applicable) with no changes during the entire treatment period.

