## 7.5 Compliance

The date and time of all IP administrations, as well as any missed doses, should be recorded in the appropriate section of the eCRF.

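### SAP 4.2.3 takes attended visits as the expected doses, so intermittently missed dosing visits do not lower the reported IP compliance

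*SAP*

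**What the plan says.** SAP 4.2.3 builds compliance from two counts. For the numerator, "the total number of dosing occasions is calculated by summing the doses taken by the subject". The denominator, the expected number of dosing occasions, is the "number of visits during treatment phase the subject attended". The ratio is "Compliance (%) = (Total number of dosing occasions/total number of dosing occasions expected) x 100". The SAP does not define the treatment phase for this purpose.

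The protocol fixes the dosing plan: "IP will be administered at weeks 0, 2, 4, 6, 8 and 10" (Duration of treatment), which is six doses at Visits 3c to 8. Protocol 4.2 runs the treatment period over those same visits and makes Visit 9 the end-of-treatment visit; Table 1 of the protocol shows no IP at Visit 9. Protocol 7.2 has IP given at the study site on treatment visits. Protocol 7.5 asks for more than attendance: "The date and time of all IP administrations, as well as any missed doses, should be recorded" in the eCRF.

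SAP 4.2.3 also summarises extent of exposure and the number of dosing occasions by treatment group. SAP section 6 does not mention the compliance denominator.

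**The concern.** Because IP is given only at visits, a subject who does not come cannot be dosed. A denominator of attended visits drops exactly those occasions, so the percentage answers a narrower question (was the subject dosed when present?) than the one its label suggests (how much of the planned treatment was given?).

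This matters because SAP 4.1 analyses efficacy data regardless of adherence or IP discontinuation. Under-dosed subjects with both biopsies stay in the primary comparison. If the result is null, a reader will ask whether the active arm received the drug, and the compliance table is a natural place to look.

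**Working it through.** The documents state no compliance figure, so there is nothing to reproduce. The check applies the SAP formulas to illustrative dosing patterns.

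**Inputs**
- Planned doses: six, at Weeks 0, 2, 4, 6, 8 and 10 (Protocol, Duration of treatment).
- Compliance = 100 × doses taken / treatment-phase visits attended (SAP 4.2.3).
- Extent of exposure = (last dosing date + 14 days) − first dosing date + 1 (SAP 4.2.3). Gaps between doses are not subtracted.
- Two readings of the denominator: Visits 3c to 8 only (the period in Protocol 4.2), or those visits plus Visit 9 when attended.

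**Why a missed visit cancels.** With Visits 3c to 8 and m missed visits, a subject dosed at every visit attended scores (6 − m)/(6 − m) = 100% for any m from 0 to 5. The share of planned doses is (6 − m)/6: 100, 83.3, 66.7, 50.0, 33.3 and 16.7%.

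**Patterns**

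| Dosing pattern | Visits 3c–8 | Visit 9 attended and counted | Share of six planned | Exposure (days) |
|---|---|---|---|---|
| All six doses | 6/6 = 100% | 6/7 = 85.7% | 100% | 85 |
| Attended and dosed at Weeks 0, 4, 10 only | 3/3 = 100% | 3/4 = 75.0% | 50.0% | 85 |
| Dosed at Weeks 0, 2, 4; no later dosing visit attended | 3/3 = 100% | 3/4 = 75.0% | 50.0% | 43 |
| All six visits attended, dosed at Weeks 0, 2, 4 | 3/6 = 50% | 3/7 = 42.9% | 50.0% | 43 |
| One dose; no later dosing visit attended | 1/1 = 100% | 1/2 = 50.0% | 16.7% | 15 |

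Exposure for Weeks 0, 4 and 10 is (70 + 14) − 0 + 1 = 85 days, the same as for a fully dosed subject. For Weeks 0, 2 and 4 it is (28 + 14) + 1 = 43 days.

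Two things follow. On the first reading, rows 2 to 4 all received three doses, yet score 100, 100 and 50% according to attendance alone. On the second reading, missed visits do lower the score, but too little (75.0% against 50.0%), and full dosing cannot reach 100% when Visit 9 is attended.

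**Rescheduling.** Protocol 7.2 lets a visit be rescheduled when IP should not be given. If the subject came both times and both attendances count, six doses over seven attendances again give 6/7 = 85.7%. The SAP does not say how to count these.

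**The case against.** The best reply is that the same section already shows what the percentage misses. The number of dosing occasions is summarised by treatment group, so a subject with three doses counts as three, and with six planned the shortfall can be read directly. SAP 4.2.1 tabulates treatment completion, discontinuation with reasons, and subjects who stop IP but stay in the study. SAP 4.1 has all data listed, and serum concentrations at Week 12 are summarised. Compliance defines no analysis set and enters neither the primary ANCOVA nor its sensitivity analyses. Protocol 7.5 sets no formula, so the two documents do not contradict each other.

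All of this stands, and it limits the consequence. It does not make the percentage right. Nor do the other outputs fully replace it: exposure is blind to mid-course gaps, PK is sampled only before the first dose and at Week 12 (SAP 3.5), and the important deviations in SAP 2.2 do not name missed doses.

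A reader might go further and infer that the compliance figure cannot show under-dosing at all, or that missed visits are the main way doses are lost. The documents support neither. Doses not given at attended visits do lower the score (6 attended, 3 dosed: 50%), and no frequency of missed visits is stated. The protocol describes other routes as well: rescheduling (7.2) and discontinuation or withdrawal (3.9.2).

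**Conclusion.** The definition is defective, but the effect is confined to a descriptive summary. With Visits 3c to 8 as the treatment phase, intermittently missed dosing visits leave compliance unchanged: 100% where 50% of planned doses were given in the Weeks 0, 4 and 10 example, with exposure at its full 85 days. If Visit 9 counts, the defect is a different one: 85.7% for a fully dosed subject. The two figures belong to alternative readings and cannot both apply. The wording of Protocol 4.2 favours the first.

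The 50% comparison uses a fixed denominator of six. It should not be read as the score every half-dosed subject ought to get: for someone who stops IP early, it depends on whether doses after stopping are regarded as expected.

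It would also be wrong to infer that the primary result is affected, or that under-dosing is hidden altogether. No estimate or p-value changes, and the dose count would show low dosing. How many subjects would be mis-scored cannot be judged from the documents. The change is still worth making, because it is cheap and needs only data that Protocol 7.5 already collects.

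**What to change.** In SAP 4.2.3, define expected dosing occasions as the scheduled dosing visits (V3c to V8) up to permanent IP discontinuation or study exit, attended or not. State that Visit 9, unscheduled visits and duplicate attendances from rescheduling do not count. The subject dosed at Weeks 0, 4 and 10 then scores 3/6 = 50%, and full dosing scores 6/6 = 100%.

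That measure alone is not enough. A subject dosed at Weeks 0, 2 and 4 who permanently stops before Week 6 has three expected doses and still scores 3/3 = 100%. One who stops IP at that point but keeps attending moves from 3/6 = 50% under the present rule to 100%. So also report doses received as a percentage of the six planned, and the share of subjects in each arm who received all six. The first measure then describes missed doses while on IP, and the other two describe total delivery, early stopping included.

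The cost is one or two SAP lines. No new data collection is needed, and the primary analysis is untouched. The downside is a somewhat less favourable compliance figure for subjects who miss visits.

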## 4.2.4 Analysis of the primary variable

All analyses of the primary endpoint will be based on the FAS.

The primary efficacy variable is the change, expressed as a ratio [Week 12 (Visit 9)/baseline] from baseline to Week 12 (Visit 9) in airway submucosal eosinophils and the primary analysis is to compare this change from baseline to Week 12 (Visit 9) for tralokinumab with placebo.

The primary efficacy variable will be evaluated through the hypothesis test:

H0: ratio (tralokinumab/placebo) equals 1 *vs*. H1: ratio does not equal 1.

The null hypothesis  $(H_0)$  is that the change in airway submucosal eosinophils at Week 12 on tralokinumab is equal to the corresponding change on placebo. The alternative hypothesis  $(H_1)$  is that the change in airway submucosal eosinophils during the 12-week double-blind treatment period is different on tralokinumab compared with the change in airway submucosal eosinophils during the 12-week double-blind treatment period on placebo.

The change in airway submucosal eosinophils in the tralokinumab group will be compared to that seen in the placebo group using an ANCOVA model.

The response variable in the model will be change, on the log-scale (expressed as a ratio) in the number of airway submucosal eosinophils from baseline to Week 12 (Visit 9) [Week 12 (Visit 9)/baseline]. The model will include treatment group as fixed effect and baseline log value as a continuous covariate. No interaction terms will be included in the model. The analysis will be performed using log-transformed data. All group comparisons from ANCOVA model will be based on Type III sums of squares. Estimated geometric means (original scale) will be presented for each treatment group as well the ratio of geometric means for the comparison of tralokinumab versus placebo (tralokinumab/placebo) and corresponding 95% confidence interval (CI).

Available values at both baseline and Week 12 (Visit 9) are required for a subject to be included in the analysis.

Summary statistics for the absolute and percentage change from baseline to Week 12 (Visit 9) will also presented.

Spaghetti plots will be presented for the primary efficacy variable (raw variable). A scatterplot will also be produced for baseline generation 4 wall area (WA) vs primary variable (using % change from baseline). The same spaghetti plots and scatter plots will be performed removing outliers. Outliers are defined as records below Q1 (first Quartile)-1.5\*IQR (Interquartile Range), and above Q3 (third Quartile) +1.5\*IQR. IQR is defined as Q3-Q1.Number of airway submucosal eosinophils and percentage change from baseline will also be listed.

## 4.2.5 Analysis of secondary variables

All secondary endpoints will be analyzed based on the FAS. Spaghetti plots will be presented for all secondary efficacy variable. A scatterplot will also be produced for baseline generation 4 WA vs ECP and separately MBP (Major Basic Protein), using % change from baseline.

#### 4.2.5.1 Blood eosinophil count

**The secondary outcome variable blood eosinophil count is:** Change, expressed as a ratio [Week12 (Visit 9)/baseline], from baseline in the blood eosinophil count to Week 12 (Visit 9).

The change from baseline to Week 12 (Visit 9) in blood eosinophil count will be compared between tralokinumab and placebo using a mixed model for repeated measures (MMRM) with treatment group, logbaseline and visit as fixed effects. Treatment-by-visit interaction will also be included. The analysis will be performed by using log-transformed data on all post baseline visits during treatment phase.

The response variable will be the change, on the log-scale (expressed as a ratio) in blood eosinophil count from baseline to Week 12 (Visit 9) [Week 12 (Visit 9)/baseline]. A restricted maximum likelihood (REML) approach will be used. All subjects with a baseline blood eosinophil count in the FAS will be included in the analysis. An unstructured variance-covariance matrix will be used to model the within-subject errors. If the model fails to converge then a compound symmetric variance-covariance matrix will be used instead. The Kenward-Roger approximation will be used to estimate denominator degrees of freedom.

Estimated geometric means ratios (original scale) will be presented for each treatment group as well the ratio of geometric means ratios for the comparison of tralokinumab versus placebo (tralokinumab/placebo) and corresponding 95% CI.

An MMRM will also be done on raw data (no log-transformation) with the absolute change from baseline as response variable. The model will include treatment group as fixed effect baseline value, and visit as fixed effects. Treatment-by-visit interaction will also be included.

Summary statistics for the absolute change from baseline at all visits in blood eosinophil count will be presented by treatment group.

Blood eosinophil count and absolute change from baseline will also be listed. 4.2.5.2 Differential sputum eosinophils

**The secondary outcome variable differential sputum eosinophils is:** Change, expressed as a ratio [Week12 (Visit 9)/baseline], from baseline in differential sputum eosinophils to Week 12 (Visit 9)

This will be analysed and summarised as described for blood eosinophil count in Section 4.2.5.1.

# 4.2.5.3 Blood and sputum free ECP

**The secondary outcome variable blood and sputum free eosinophils cationic protein** (ECP) is: change, expressed as a ratio [Week12 (Visit 9)/baseline] in blood free ECP concentration from baseline to Week 12 (Visit 9); change, expressed as a ratio [Week12 (Visit 9)/baseline] in sputum free ECP concentration from baseline to Week 12 (Visit 9)

This will be analysed and summarised and described for the primary efficacy variable in Section 4.2.5.1.

# 4.2.6 Analysis of exploratory variables

Change from baseline analysis will be performed for each exploratory variable detailed in Sections 3.2.3 and 3.3.1, and summarized using descriptive statistics and graphical displays (spaghetti plots, and scatter plots for some variables, see below).

Spirometry variables defined in Section 3.2.3.4 will also be summarised as per Section 4.2.5.1 for the descriptive statistics only – there won't be any MMRM. The analysis will be based on raw data – there won't be any log-transformation before the analysis.

# 4.2.6.1 Scatter plots

The following scatter plots will be produced: baseline generation 4 WA% versus:

- FEV1 (absolute change from baseline)
- FEV1 (% change from baseline)
- AHR PD20 (baseline value)
- AHR PD20 (absolute change from baseline)
- AHR PD20 (% change from baseline)
- Generation 4 CT Lumen area, Airway LAGeneration 4 (% change from baseline)
- Generation 4 CT Wall area, Airway WAGeneration 4 (% change from baseline)
- Generation 4 CT WA%, Airway WAFGeneration 4 (% change from baseline)
- Generation 5CT Lumen area, Airway LAGeneration 5(% change from baseline)
- Generation 5CT Wall area, Airway WAGeneration 5 (absolute change from baseline)
- Generation 5CT WA% Airway WAFGeneration 5(% change from baseline)

### 4.2.6.2 Subgroup analyses

The consistency of treatment effect on  $FEV_1$  and Airway LA Generation 4 (% change from baseline) parameters across different subgroups (high. vs. low baseline Generation 4WA% (median cut-off)) will be explored using descriptive statistics for continuous data based on the FAS.

# 4.2.6.3 Exacerbation

Exacerbations will be listed only.

# 4.2.7 Serum Biomarkers and immunology

Serum biomarkers and IgE will be summarised, for each parameter, by visit and treatment group, using descriptive statistics for continuous data.

The serum biomarkers include, but are not limited to, periostin; DPP4.

# 4.2.8 Analysis diary data variable(s)

All diary data parameters will be summarized on the FAS using the methodology described in section 4.2.5.1 for the descriptive statistics only – there won't be any MMRM. The diary data analysis will be based on raw data – there will not be any log-transformation before the analysis.

### 4.2.8.1 Asthma symptoms

**The key secondary outcome variable**: Change from baseline in bi-weekly mean daily asthma symptom total score (combined daytime and night-time score as captured in the Asthma Daily Diary).

The absolute change from baseline in bi-weekly means (daily asthma symptom total score, daytime score, and night-time score) at Week 12 will each be summarized as described in Section 4.2.5.1 for the descriptive statistics only – there won't be any MMRM.

The proportion of asthma symptom-free days up to Week 12 will also be summarized.

# 4.2.8.2 ACQ-6 defined asthma control

Percent change in mean score from baseline for ACQ-6 (and each of the individual questions) will be summarized as described in Section 4.2.5.1 for the descriptive statistics only – there won't be any MMRM.

The number and percentage of subjects achieving mean ACQ-6  $\leq 0.75$ , 0.75 < mean ACQ-6 <1.5 and mean ACQ-6 of  $\geq 1.5$  at Week 12 will be summarized by treatment. Additionally, the number and percentage of subjects achieving an improvement, no change, or deterioration as per Section 3.3.1.5, will also be summarized by treatment.

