## 5.3.2.2 Asthma Control Questionnaire (ACQ-6)

The Asthma Control Questionnaire (ACQ)-6 is a shortened version of the ACQ that assesses asthma symptoms (night-time waking, symptoms on waking, activity limitation, shortness of breath, wheezing, and short-acting  $\beta_2$ -agonist use) omitting the FEV₁ measurement from the original ACQ score.

Subjects will be asked to recall how their asthma has been during the previous week by responding to 1 question regarding their BD use, and 5 questions pertaining to their asthma symptoms. Subjects will be instructed to count each use of nebulizer as 2 puffs of inhalers.

Questions are weighted equally and scored from 0 (totally controlled) to 6 (severely uncontrolled). The mean ACQ-6 score is the mean of the responses. Mean scores of  $\leq 0.75$  indicate well-controlled asthma, scores between 0.75 and  $\leq 1.5$  indicate partly controlled asthma, and a score >1.5 indicates uncontrolled asthma (Juniper EF et al 2006). Individual changes of at least 0.5 are considered to be clinically meaningful.

ACQ-6 will be completed at the study site using eDiary in accordance with the schedule provided in Table 1.

## 5.3.2.3 Sino-Nasal Outcome Test - 20

Sino-Nasal Outcome Test -20 (SNOT-20) is a health-related and disease specific instrument for assessing quality of life for rhinosinusitis. This questionnaire contains 20 questions divided across five subgroups (nasal symptoms, paranasal symptoms, sleep-related symptoms, and social and emotional impairment). Subjects will rate their experiences during the previous 2 weeks and score each question on a six-point scale (0-no problem, 5-most serious problem) and in addition, they will mark which of the five items they consider to be the most important.

Total score will be calculated for each assessment. SNOT-20 will be completed by the subject at study site using a paper based tool in accordance with the schedule provided in Table 1. Completed paper questionnaires will be kept in subject's chart for SDV and data from the questionnaire transcribed into the respective fields of eCRF.

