### Home peak expiratory flow (morning and evening)

Biweekly mean absolute changes from baseline in morning and evening PEF will be calculated.

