#### 3.1.2 Absolute and percent change from baseline

Absolute change from baseline outcome variables is computed as

(post-randomization value – baseline value).

Percent change from baseline is computed as

((post-randomization value – baseline value) / baseline value)  $\times$  100%.

Ratio of post-randomization value to baseline value is computed as

(post-randomization value / baseline value).

For the analysis of ratios, a log transformation is required. If either the post-randomization value or the baseline value is missing, then the absolute or percent change from baseline or the ratio value will also be set to missing.

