#### 3.3.1.5 Asthma Control Questionnaire (ACQ-6)

In the ACQ-6 questionnaire the subjects are asked to recall the status of their asthma during the previous week with regards to symptom and use of short acting  $\beta$ -agonists. The questionnaire include questions on

- 1. Awoken at night by symptoms
- 2. Limitation of normal daily activities
- 3. Waking in the morning with symptoms

- 4. Dyspnoea
- 5. Wheeze
- 6. Daily rescue medication

The questions of the ACQ-6 are measured on a 7-point scale scored from 0 (totally controlled) to 6 (severely uncontrolled). The ACQ-6 score is computed as the un-weighted mean of the responses to the 6 questions. If response to any of the questions is missing, the ACQ-6 score will be missing.

The outcome variable for the ACQ-6 will be the change in mean score from baseline to each of the post-randomization assessments. The change from baseline for each question will also be calculated.

Other variables based on ACQ-6 to report include:

- ACQ-6-responder (Yes=1/No=0)
  - Responder: Change from baseline ACQ-6 score  $\leq$  -0.5
  - $\circ$  Non-responder: Change from baseline ACQ-6 score > -0.5
- ACQ-6-response (Improved/No Change / Deterioration)
  - Improvement: Change from baseline ACQ-6 score  $\leq$  -0.5
  - $\circ$  No change: -0.5 < Change from baseline ACQ-6 score < 0.5
  - Deterioration: Change from baseline ACQ-6 score  $\geq 0.5$
- Subjects asthma control as measured by ACQ-6 score:
  - Well controlled : ACQ-6 score  $\leq 0.75$
  - $\circ$  Partly controlled: 0.75 < ACQ-6 score < 1.5
  - Not well controlled: ACQ-6 score  $\geq 1.5$

The ACQ-6-responder, the ACQ-6-response, and subject asthma control variables will be analysed only considering non-missing ACQ-6 values.

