The primary and secondary variables will be analysed using geometric means. Both the difference in number and the % change or ratio will be reported, but the statistical analysis will only be based on the ratio. All hypothesis testing will be reported using 2-sided tests. P-values will be rounded to 4 decimal places. No adjustment for multiplicity will be performed and nominal p-values will be reported.

For the efficacy analyses except PRO/ SNOT-20 data, if the value of the ratio of Week 12 to baseline is zero and both Week 12 and baseline are not missing, the ratio will be replaced, for the analysis of ratio only (including for descriptive statistics), by half the smallest observed ratio among the randomized subjects with non-zero values (both treatment arms). For the corresponding non descriptive analyses on the ratio, values of baseline equal to zero were replaced by half the smallest observed value among the subjects with non-zero for the calculation of the baseline logtransformed covariate,

For the efficacy analyses except PRO/ SNOT-20 data, if the baseline value is zero, the baseline will be replaced, for the analysis of ratio to baseline or percent change from baseline only (including for descriptive statistics), by half the smallest observed value among the randomized subjects with non-zero values and among all records (baseline and post baseline

for both treatment arms). If both the baseline and post-baseline record are zero, then the percent change is zero.

QQ plots of residuals of the primary and secondary efficacy analysis models (both on absolute change and log-transformed ratio) will be created.

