#### 4.2.8.5 Home PEF (morning and evening)

The percent change from baseline in bi-weekly mean morning and evening PEF will each be summarized as described in Section 4.2.5.1 for the descriptive statistics only – there won't be any MMRM.

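### SAP 4.2.8.2 summarises ACQ-6 and its 0-6 items as percent change, which does not match the point-scale outcome variable and is undefined for items that start at 0

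*SAP*

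**What the plan says.** - SAP 4.2.8.2 gives the ACQ-6 summary as: "Percent change in mean score from baseline for ACQ-6 (and each of the individual questions) will be summarized". The format follows the descriptive part of SAP 4.2.5.1, which itself uses absolute change.
- SAP 3.3.1.5 defines the variable differently: "The outcome variable for the ACQ-6 will be the change in mean score from baseline to each of the post-randomization assessments". It also calculates a change for each question and sets the response categories at -0.5 and +0.5 points.
- Protocol 5.3.2.2 gives the clinical yardstick in points: "Individual changes of at least 0.5 are considered to be clinically meaningful".
- On the scale, SAP 3.3.1.5 says: "The questions of the ACQ-6 are measured on a 7-point scale scored from 0 (totally controlled) to 6 (severely uncontrolled".
- SAP 3.1.2 defines percent change as 100 times ("post-randomization value – baseline value) / baseline value", so baseline is the divisor.
- The only rule for a zero baseline, in SAP 4.1, begins: "For the efficacy analyses except PRO/ SNOT-20 data, if the baseline value is zero, the baseline will be replaced". The last sentence of that paragraph sets percent change to zero when baseline and post-baseline are both zero.
- SAP 4.1 says exploratory efficacy variables are summarised as absolute and percent change. SAP section 6 says absolute, percent and ratio for all exploratory endpoints.

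**The concern.** There are two separate problems.

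The first is the scale. The ACQ-6 variable, its clinically meaningful change and its response categories are all in points, but the section that specifies the table names percent. The neighbouring section, SAP 4.2.8.1, names absolute change for the symptom scores, so the wording in 4.2.8.2 looks deliberate. A programmer working from it alone would build a percent table.

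The second is the zero divisor. A baseline answer of 0 on one question, such as no night waking, is ordinary even in a patient whose overall control is poor. Percent change then has no value, and the SAP's repair is switched off for PRO data. The subjects lost are not a random subset: from 0 an item can only stay the same or get worse.

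At stake is whether the ACQ-6 tables can be read alongside the rest of the ACQ-6 reporting, and whether the item tables leave out one kind of outcome.

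**Working it through.** The plan gives no figure for this point, so there is none to reproduce. The check applies the SAP 3.1.2 formula to the ACQ-6 scale.

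**1. Percent against points.** A 0.5-point improvement in mean score is -0.5/baseline × 100:

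| Baseline mean score | Percent change |
|---|---|
| 1.0 | -50.0% |
| 1.5 | -33.3% |
| 2.0 | -25.0% |
| 3.0 | -16.7% |
| 4.0 | -12.5% |

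No single percentage stands for 0.5 points.

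The two summaries can also differ in sign. Take illustrative baselines 1, 1, 4, 4 and post values 1.5, 1.5, 3, 3:
- Mean absolute change = (0.5 + 0.5 - 1 - 1)/4 = -0.25, an improvement.
- Mean percent change = (50 + 50 - 25 - 25)/4 = +12.5%, a worsening.

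**2. Can an item be 0 at baseline?** Protocol 3.1 requires ACQ-6 of at least 1.5 at Visit 1 or Visit 2, but that applies to the mean. A mean of 1.5 is an item sum of 6 × 1.5 = 9, and two items can reach 9 because 2 × 6 = 12. Up to four of the six items can therefore be 0. Baseline is taken later, at Visit 3c (SAP 3.1.1). A mean score of 0 at Visit 3c is possible but unlikely, so the zero problem is essentially one of items.

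**3. Which pairs are lost?**

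| Item pair | PRO exclusion covers the whole SAP 4.1 paragraph | Last sentence applies to PRO data as well |
|---|---|---|
| 0 to 0 | undefined | 0% |
| 0 to positive | undefined | undefined |

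The text does not settle which reading is meant. Subjects going from 0 to a positive score are lost under both.

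**4. How many?** The documents give no item distributions, so the following are assumptions: item score normal with mean 1.5 to 2.5 and SD 1.4, rounded and clipped to 0-6, correlation between visits 0.5 to 0.7, no true change.

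P(baseline = 0) = Φ((0.5 - mean)/1.4):
- mean 1.5: Φ(-0.714) = 0.238
- mean 2.5: Φ(-1.429) = 0.077

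P(0 to positive) = P(baseline = 0) × (1 - share that stay at 0), with that share taken from the bivariate normal:

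| Mean | Correlation | Baseline 0 | Share staying at 0 | 0 to positive |
|---|---|---|---|---|
| 1.5 | 0.5 | 0.238 | 0.47 | 0.126 |
| 1.5 | 0.7 | 0.238 | 0.59 | 0.097 |
| 2.5 | 0.5 | 0.077 | 0.29 | 0.054 |
| 2.5 | 0.7 | 0.077 | 0.44 | 0.043 |

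With 40 randomised per arm, that is about 40 × 0.043 = 1.7 to 40 × 0.126 = 5.0 worsened subjects missing per item and arm. If 0-to-0 pairs are lost too, it is 40 × 0.077 = 3.1 to 40 × 0.238 = 9.5.

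**The case against.** The strongest reply is that absolute change is already planned. SAP 4.2.6 calls for a change-from-baseline analysis of every exploratory variable in SAP 3.3.1, which includes ACQ-6. SAP 4.1, section 6 and the 4.2.5.1 template all point the same way. SAP 4.2.8.2 does not say that percent is the only summary; where the SAP wants that, as for the airway CT parameters in 3.2.3.2, it says so. All data are to be listed. Percent change also has a basis in the protocol, since section 8.4.4.4 says it will be calculated.

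This stands as a limit on the point, and it rules out three stronger readings that a reader might infer:

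- **That worsening from a symptom-free item is never shown.** Not supported. The provisions above imply that absolute changes per question are also summarised, and the individual data are listed. The omission affects the percent-change item tables.
- **That ACQ-6 results cannot be read against the 0.5-point criterion.** Not supported. That criterion concerns individual changes, and the second paragraph of 4.2.8.2 tabulates improvement, no change and deterioration on the point scale.
- **That Home PEF has the same defect.** SAP 4.2.8.5 specifies "The percent change from baseline in bi-weekly mean morning and evening PEF", while the protocol says "Biweekly mean absolute changes from baseline in morning and evening PEF will be calculated". But Protocol 8.4.4.4 covers PEF and also calls for percent change, and a PEF baseline of zero does not arise in practice. Which summary comes first is largely preference.

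The counts rest on assumed distributions, and nothing here shows a difference between arms. Randomisation makes the loss similar in both on average, apart from chance imbalance and any treatment effect on zero-baseline items.

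The objection does not supply a rule for zero item baselines, and it does not remove the conflict between 4.2.8.2 and the rest of the SAP.

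**Conclusion.** The point holds as an inconsistency plus an arithmetic gap. SAP 4.2.8.2 names a summary that differs from the variable defined in 3.3.1.5 and from the general statements in 4.1 and section 6. That follows from the text alone. For the items, percent change has no value when baseline is 0 and the score then rises, and no SAP rule covers this. That needs no assumption either.

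The size does need assumptions: 8% to 24% of subjects with a zero baseline on a given item, and 4% to 13% going from 0 to positive. Both ranges would move with other item means, spread or correlation.

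The importance is low. ACQ-6 is exploratory and summarised descriptively without a model. The response and control categories stay on the point scale, and the primary and secondary analyses and the power do not depend on it.

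**What to change.** In SAP 4.2.8.2, change the word Percent to Absolute for the ACQ-6 mean score and each question, and drop percent change for the individual questions. Because Protocol 8.4.4.4 and SAP section 6 mention percent change in general terms, add a line to section 6 recording that it is not produced for ACQ-6 items. Every baseline and post-baseline pair then has a value, and 0.5 points means the same at every baseline.

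The cost is a one-word edit, a short note and a change of table shell. No new data are needed, and no sample-size or power figure changes. SAP 4.2.8.5 on Home PEF needs no change for this reason.
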